This pilot study has 2 components: 1) a cross-sectional assessment designed to estimate the prevalence of anaemia leading to donor deferral, the prevalence of ID and the prevalence of IDA among first-time donors, and 2) a longitudinal 2-arm parallel groups trial among first-time voluntary donors that compares haemoglobin levels at 4 months among those with ID or IDA who receive iron supplementation to those without ID or IDA who do not receive iron supplementation. The primary outcome will be haemoglobin levels at 4 months. Participants will be followed for a total of 6 months with study visits at 2, 4 and 6 months after the baseline assessment. Blood draws for FBC, peripheral film comment, Malaria rapid test and ferritin assessment and the administration of a structured questionnaire will occur at all follow-up visits.

The parallel group's component is designed as a non-inferiority trial for haemoglobin levels at 4 months. At baseline, the 2 groups will be determined based on the need for iron supplementation: all individuals with ID or IDA, who satisfy our eligibility criteria regardless of deferral status, will receive iron supplements while all others will not. While a high prevalence of ID and IDA is expected, enrolment will be staggered so that an equal number of participants from each group are enrolled from each site with at least 1 participant who is found to be ID or have IDA. If there are more potential participants in one group at some site, randomization will be used to select the individuals to enroll in the trial to maintain balance over time. The extent of adherence is a central question for this study, and it is also unclear if the haemoglobin deficiency can be improved above what is seen in the control group, hence it is not hypothesized that those receiving

iron supplementation will have higher levels of haemoglobin at 4 months. The hypothesis about iron supplementation intervention is that it will improve haemoglobin levels to near that seen among those who were not deferred. If haemoglobin levels are higher in those receiving iron supplementation the intervention would also be deemed a success. Hence a non-inferiority trial is most appropriate for this hypothesis.

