The parallel group's component is designed as a non-inferiority trial for haemoglobin levels at 4 months. At baseline, the 2 groups will be determined based on the need for iron supplementation: all individuals with ID, IDA or low haemoglobin (gender specific values), who satisfy our eligibility criteria regardless of deferral status, will receive iron supplements while all others will not. While a high prevalence of ID and IDA is expected, enrolment will be staggered so that an equal number of participants from each group are enrolled from each site with at least 1 participant who is assigned to iron supplementation. If there are more potential participants in one group at some site, randomization will be used to select the individuals to enroll in the trial to maintain balance over time. The extent of adherence is a central question for this study, and it is also unclear if the haemoglobin deficiency can be improved above what is seen in the control group, hence it is not hypothesized that those receiving iron supplementation will have higher levels of haemoglobin at 4 months. The hypothesis about the iron supplementation intervention is that it will improve haemoglobin levels to near that seen among those who did not receive iron supplementation. If haemoglobin levels are higher in those receiving iron supplementation the intervention would also be deemed a success. Hence a non-inferiority trial is most appropriate for this hypothesis.

Selection of the margin is a critical component of a non-inferiority trial. Here, we specify a margin of 1 g/dL for haemoglobin levels at 4 months. Under a collection of reasonable assumptions, this margin will ensure that the majority of those with low haemoglobin at screening will have haemoglobin levels at 4 months above the threshold for anaemia and should therefore qualify as donors. To see this, assume that half of donors are anaemic at screening (using the thresholds for anaemia of 13 g/dL for men and 11.5 g/dL for women). A simple calculation finds that if we assume haemoglobin levels are normally distributed (which is a reasonable assumption based on observed distributions for haemoglobin in unselected individuals in West Africa) and the standard deviation of screening haemoglobin levels is 1.89 g/dL (this estimate will be described below) then the mean haemoglobin level among men who are deferred is 11.5 g/dL and the mean haemoglobin level among men who are not deferred is 14.5 g/dL (these values for

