women are 10.0 g/dL and 13.0 g/dL). If we assume that the haemoglobin level among those who are not deferred is the same 4 months later then a margin of 1 g/dL implies a mean haemoglobin level among those with anaemia at screening of at least 13.5 g/dL for men and 12.0 g/dL for women. Thus, the mean haemoglobin level after 4 months of iron supplementation among those who should have been deferred will exceed the threshold for anaemia and consequently, if the distribution of haemoglobin levels is symmetric, the majority of those who were anaemic at screening would qualify as donors (in fact at least 60.4% would pass the threshold for both sexes if this distribution is normal). Note that the threshold for the copper sulphate test used for women is 12 g/dL, not 11.5 g/dL, so under these assumptions 50% of women would pass the copper sulphate test. Nonetheless, since well over 50% of donors are men the majority of deferred donors would pass the copper sulphate test. It is likely that fewer than half of all donors will be anaemic at screening. In this case the difference in the means between those with anaemia and those without anaemia will be larger, the gain in haemoglobin levels in the anaemic group will be larger and the proportion of donors who would be deferred at screening but would not be deferred after 4 months of iron supplementation will be even larger. It is possible that the difference between the 2 groups is smaller than the margin at screening. This seems unlikely since the 2 groups are defined by a threshold for haemoglobin levels, but if the standard deviation of haemoglobin levels is 0.62 then the difference between the groups among men would be less than the margin under the assumptions of the previous paragraph (this standard deviation is less than one third of the standard deviation used for design). To address this, when enrolment reaches 50% of the total planned sample size, the statisticians supporting the trial at the data coordinating centre (DCC) will compute the standard deviation of haemoglobin levels at screening and revisit the margin calculation and the sample size. If the standard deviation is low enough so that the difference between the groups is less than the margin, then the study will be overpowered for the current margin and a smaller margin will be selected so that the trial is still testing for differences at 4 months that exceed the screening difference. Any changes to the study design based on these analyses will be discussed with the DSMB.

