**Table 2: Precision of prevalence estimates for ID and IDA.**

Prevalence	Error Margin	95% Confidence Interval
0.2	0.046	0.15, 0.25
0.3	0.053	0.25, 0.35
0.4	0.056	0.34, 0.46
0.5	0.057	0.44, 0.56

**Parallel groups study:** The primary outcome for this portion of the study is haemoglobin levels at 4 months. Formally the null hypothesis for this outcome is inferiority of treatment of low haemoglobin with iron supplementation among those with

low haemoglobin at screening to no treatment among those without low haemoglobin at screening. The non-inferiority margin is fixed at a value of 1.0 g/dL. Based on recent work in West Africa, the DCC has access to haemoglobin measurements from 1548 individuals between the ages of 17 and 60 who weigh at least 50 kg. Among these individuals the standard deviation of haemoglobin was 1.89 g/dL (the mean was 13.4 g/dL). These individuals did not pass the strict screening criteria used by the NBSG, so this estimate might be slightly inflated and so our power calculations may be somewhat conservative. We specify an alpha level of 0.025 and require power of at least 85%. With these values we can determine the number of participants per arm if we assume a value for the true difference between the groups (the absolute value of this difference must be less than our margin and will generally be negative when the margin is positive to be consistent with the lack of superiority of iron supplementation). Table 3 presents the number of participants per arm under these assumptions for a selection of values for the true difference. We assume that the true difference is -0.3 g/dL and obtain a sample size of 131 participants per arm. If the true difference is larger than -0.3 g/dL (e.g., if there is no difference) then the power will exceed 85%. To allow for loss to follow-up and some participants requiring iron supplementation due to incident anaemia, ID or IDA the sample size has been increased to 292.

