#### Primary analysis

The analysis for the primary outcome of haemoglobin levels at 4 months will be conducted using a linear model with haemoglobin levels at 4 months as the response variable. It is unlikely that there is a need to transform the response variable as haemoglobin levels are usually symmetrically distributed with tails that decay at rates consistent with the normal distribution. However, if informal univariate assessments of normality (e.g., qq-plots) indicate strong departures from these expectations, the Box-Cox transformation will be used to select a transformation. The set of explanatory variables will be group membership (i.e., received iron supplementation at enrolment or not), screening haemoglobin, sex, and age. A 1-sided t-test for the regression coefficient associated with group membership will be conducted with a significance level of 0.025 to test the inferiority hypothesis. This analysis will exclude individuals who did not receive iron supplementation at enrolment but received it during follow-up due to changes in ferritin or haemoglobin values. The frequency of this will be closely tracked and if more than 10% of participants in the group initially not receiving iron supplementation receive iron supplementation during follow-up, alternative analysis approaches will be considered and presented to the DSMB.

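### The 1 g/dL margin and the 131 per arm are set for the raw gap in 4-month mean Hb, but the primary test is on a group coefficient adjusted for screening Hb, in arms formed partly by screening Hb

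*SAP*

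**What the plan says.** **Margin.** SAP 1.2 (Design) and the Protocol's Design section argue from group means at 4 months. With an unchanged mean of 14.5 g/dL in men who were not deferred, "a margin of 1 g/dL implies a mean haemoglobin level among those with anaemia at screening of at least 13.5 g/dL for men". SAP 2.4 then states: "The non-inferiority margin is fixed at a value of 1.0 g/dL".

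**Sample size.** SAP 2.4: "We assume that the true difference is -0.3 g/dL and obtain a sample size of 131 participants per arm". The column heading of Table 3 in both documents is the treated-minus-control difference in mean Hb, and the SD is the total SD of 1.89 g/dL.

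**Test.** SAP 7.2.1 gives the covariates: "The set of explanatory variables will be group membership (i.e., received iron supplementation at enrolment or not), screening haemoglobin, sex, and age". It continues: "A 1-sided t-test for the regression coefficient associated with group membership will be conducted with a significance level of 0.025". The Protocol's Quantitative Data Analysis section has the same model.

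**Arms.** SAP 2.2 says that treatment is not randomised. SAP 1.2 forms the arms by need: "all individuals with ID, IDA or low haemoglobin (gender specific values), who satisfy our eligibility criteria regardless of deferral status, will receive iron supplements". The Protocol's rule is narrower: "all individuals with ID or IDA, who satisfy our eligibility criteria regardless of deferral status, will receive iron supplements while all others will not".

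**Analysis set.** SAP 7.2.1 says of controls who start iron later: "This analysis will exclude individuals who did not receive iron supplementation at enrolment but received it during follow-up". If more than 10% of controls do so, other approaches go to the DSMB. SAP 7.2.3 adds a sensitivity analysis that keeps them as controls, and a weighting analysis whose model includes screening Hb and ferritin.

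**The concern.** In a randomised trial, adding baseline Hb to a linear model leaves the target unchanged and gains precision. Here arm and screening Hb are linked by design; in the SAP's own example the groups start about 3 g/dL apart. The adjusted coefficient compares an iron and a control participant with the same screening Hb. The margin concerns something else: whether the iron group as a whole ends within 1 g/dL of the controls, so that most previously anaemic donors would qualify.

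Read as an effect of iron at a given screening Hb, a limit of -1 g/dL asks only that iron not lower Hb by that much. The stated hypothesis is that iron brings Hb close to control levels. This is the pilot's only formal non-inferiority conclusion, so its meaning and its quoted power are both at stake.

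**Working it through.** **Inputs from the documents.** Margin 1.0 g/dL, one-sided alpha 0.025, power at least 85%, SD 1.89, true difference -0.3 (SAP 2.4); thresholds 13 and 11.5 g/dL with half of donors anaemic (SAP 1.2); trial entry only at Hb of 10 g/dL or more (SAP 3.1); iron deficiency (ID) 41.3% (SAP 2.4) or 68.8% (Protocol, Problem Statement).

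**Assumed, because the documents do not give them.** Slope b of 4-month on screening Hb (equal to the correlation r if the SD is unchanged); 70% men; Hb-ferritin correlation 0.2 or 0.5; whether ferritin predicts later Hb beyond screening Hb.

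**1. The plan's own figures.**
- n = 2 x 1.89² x (1.960 + 1.036)² / (1.0 - 0.3)² = 130.9, so 131. The other Table 3 rows (65, 80, 101, 179) also reproduce.
- 131/0.9 = 145.6, so 146 per arm and 292 in total.
- Margin example: 1.89 x √(2/π) = 1.508, giving 13 ∓ 1.508 = 11.5 and 14.5.

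The formula has no covariate term. It is the unadjusted two-mean calculation.

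**2. What the adjusted coefficient measures.** In the margin example the screening gap is 2 x 1.508 = 3.016 g/dL, so adjusted coefficient = raw 4-month gap + 3.016 x b.

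**3. Raw gap exactly at the margin (-1.0), arms split purely on Hb, all controls kept.** R² of group on screening Hb is 2/π = 0.637, so the variance inflation factor is 1/(1 - 0.637) = 2.75. SE = 1.89 x √(1 - b²) x √(2 x 2.75/131). Pass rate = Φ((coefficient + 1)/SE - 1.96).

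| b | Adjusted coefficient | SE | Pass rate (nominal 2.5%) |
|---|---|---|---|
| 0.3 | -0.10 | 0.370 | 69% |
| 0.5 | +0.51 | 0.335 | 99% |
| 0.7 | +1.11 | 0.277 | about 100% |

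Simulation of the linear model agrees (68.5%, 99.3%, 100%).

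**4. SAP arms, zero iron effect, all controls kept** (the control-inclusive set of SAP 7.2.3). Simulated with 131 per arm and 41.3% ID, except in the last row:

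| Hb-ferritin corr. | r | Ferritin predicts later Hb | Sex-and-age gap | Adjusted coefficient | Adjusted test passes |
|---|---|---|---|---|---|
| 0.2 | 0.7 | no | -1.35 | 0.00 | 99.7% |
| 0.2 | 0.7 | yes | -1.45 | -0.14 | 98.2% |
| 0.5 | 0.5 | yes | -1.48 | -0.68 | 22.3% |
| 0.5 (68.8% ID, Hb centred on 13.4) | 0.5 | yes | -1.59 | -0.87 | 7.6% |

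In the first two rows, a test adjusted for sex and age only passes 0.0% of the time.

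**5. SAP arms, zero iron effect, planned exclusion.** Controls with low Hb at month 2 or 4 are dropped. In the first example of step 4, the adjusted coefficient moves from 0.00 to about -0.70 and the pass rate falls from 99.7% to about 23%. In the settings checked, inert iron passes about:
- 0-16% at r = 0.5
- 8-70% at r = 0.7
- 59-96% at r = 0.8
- at least 99% at r = 0.9

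A wider grid of 80 settings gives 0-27%, 1-81% and 23-99% at r = 0.5, 0.7 and 0.8, and 98-100% at r of 0.9 or more. The low ends move by several points with how the month-2 value is modelled. More than 10% of controls are usually dropped, which triggers the referral to the DSMB.

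**6. Sample size on the adjusted scale, arms split purely on Hb, true adjusted difference -0.3.** n = 130.9 x (1 - r²)/(1 - 2/π) = 270.2, 183.7, 129.7 and 68.4 per arm at r = 0.5, 0.7, 0.8 and 0.9. With 131 per arm, power is 55%, 72% and 85% at r = 0.5, 0.7 and 0.8. So 131 can be too few or too many.

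**The case against.** **Tempting stronger reading.** A reader might infer that the plan as written would often declare an inert supplement non-inferior. The documents do not support that as a general statement. The high pass rates in step 4 keep all controls, whereas SAP 7.2.1 drops those who start iron. With that exclusion, rates run from near zero to near 100%, depending on an r that no section gives. Where many controls are dropped, the DSMB referral takes the trial off its default analysis. This objection stands, and the rates are illustrations, not probabilities. The exclusion does not repair the mismatch: it adds a second, outcome-dependent shift in the other direction.

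**Other points on that side.**
- The null value is not missing. SAP 2.4 states the inferiority null and fixes the margin, so SAP 7.2.1 lacks only a cross-reference.
- The 131 is not an arithmetic error; it reproduces exactly.
- Under the Protocol's ID-or-IDA arms (IDA is iron deficiency anaemia), Hb does not itself define the arms, and the starting gap and the distortion are smaller.
- Dropping screening Hb is no cure for confounding. Where regression to the mean alone brings the no-effect gap inside the margin (-0.68 to -0.99), the sex-and-age test also passes inert iron, up to 30% of the time under SAP arms.
- This is a pilot with feasibility, acceptability and donation endpoints.

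All of these limit the size of the point or the choice of remedy. None puts margin and test on the same scale. The weighting analysis in SAP 7.2.3 and the change-in-Hb model in SAP 7.2.2 also condition on screening Hb. The review at 50% enrolment revisits the margin and sample size from the screening SD, not the model.

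**Conclusion.** The mismatch is real and should be corrected before database lock. Margin, assumed difference and sample size describe the raw difference in 4-month means; the primary test describes a difference at equal screening Hb. Because arms and screening Hb are linked by design, these are different quantities. A pass on the adjusted coefficient would not establish the stated hypothesis, and the 85% power does not apply to the planned test.

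This conclusion needs no assumption about r. Its numerical size does. It is large with arms split purely on Hb and all controls kept, and ranges from negligible to near-certain false passing under the planned exclusion. The documents support neither a single false-pass rate nor the view that the adjusted model must be abandoned.

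**What to change.** In SAP 7.2.1 and the Protocol's Quantitative Data Analysis section, put the margin, sample size and test on one scale and cross-reference the -1.0 g/dL null from SAP 2.4. Either route resolves the mismatch:

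- **(a) Test the quantity that the margin describes.** Make the primary contrast the iron-minus-control difference in mean 4-month Hb, adjusted for sex and age only, against -1 g/dL. Label it a non-causal benchmark against donors who did not need iron at enrolment. Keep the screening-Hb-adjusted model as supportive and do not compare it with the 1 g/dL margin. Report the control-inclusive set of SAP 7.2.3 alongside the SAP 7.2.1 exclusion set, because dropping controls who become anaemic widens the raw gap. Cost: baseline-adjustment precision is lost, though the 131 never assumed it, and the contrast stays confounded by design.
- **(b) Keep the adjusted model.** Re-derive and justify the margin, assumed difference, residual SD and stated power on that scale, allowing for the correlation between arm and screening Hb. Cost: an assumed r must be stated, and the power restated.

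Both are changes of wording and model specification and need no new data. SAP 1.1 allows updates until database lock. The differing arm definitions in the Protocol and SAP should be reconciled as a separate point.

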## **Study site and Population**

The NBSG SZBC located in the capital Accra annually collects voluntary blood donations from 200-300 blood donor groups that are categorized as (i) religious organizations, (ii) educational institutions, (iii) corporate institutions, (iv) organized community groups, (v) walk-in blood donors and (vi) mass/media events. Data for the prevalence of deferral assessment will be collected from all prospective voluntary blood donors within the catchment areas of the SZBC. The prevalence study of ID and IDA as well as the parallel groups trial will be restricted to first-time donors. The parallel groups trial will be restricted to voluntary donors. Generally, prospective voluntary blood donors are healthy, unlikely to be severely anaemic and are more likely to be male.

The study population will be all adults between the ages of 17 and 60 years who visit blood donation sites at the time of recruitment. A stringent screening and selection process is performed to evaluate the suitability of prospective donors. This is essential to guarantee the safety and adequacy of the blood supply; protecting the wellbeing of the recipients of transfusion as well as the fitness of the donors while ensuring that qualified donors are not deferred needlessly.

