## **Stratification and Sampling**

The SZBC contributes to the blood service needs of the Western, Central, Greater Accra, Eastern and the Volta Regions of Ghana. In 2018 and 2019, the SZBC attended to an average of 550 prospective voluntary blood donors a week, including 80 walk-in donors. Out of this number, the study will recruit all participants (who fall within the inclusion criteria) reporting per day for up to 6 months until the sample size is attained. Eligible participants will form the sampling frame for the study.

Donors will be informed about the trial and the prevalence study of ID and IDA. Due to a need to recruit approximately equal numbers of participants in the 2 groups in the trial, donors who fail the copper sulphate test will be disproportionately approached for participation. This creates a stratification of donors by status with regard to the outcome of the copper sulphate test. Within these strata the proportion of donors who are ID and IDA will be determined. The estimates of these proportions within strata will be unbiased but if one simply averages over the strata, we expect that the estimates of the proportion who are ID or IDA will have positive bias. However, since we will have estimates of the proportion of donors who fail the copper sulphate test, we can post-stratify the proportions of donors who are ID or IDA by the proportion of donors who fail the copper sulphate test.

Out of the sampling frame, participants will be purposively sampled for FGDs. In all there will be ten FGDs i.e., two groups (male-only and female-only) selected to represent each of the five NBSG voluntary blood donation categories (excluding mass/media event donors), and with each group composed of both first-time and repeat donors. In-depth interviews will also be conducted with blood donation staff and medical officers responsible for blood donation.

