### 2.2 Randomization

There is no randomization in the cross-sectional component. In the parallel groups' component, the 2 groups will be determined based on the need for iron supplementation, so the treatment is not assigned by randomization.

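### Enrolment is balanced between groups within each recruitment site but the primary model omits site, which may cost a little precision if 4-month haemoglobin varies by site

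*SAP*

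**What the plan says.** **Enrolment.** The Protocol (Methodology, Design) states that "enrolment will be staggered so that an equal number of participants from each group are enrolled from each site". The SAP (1.2 Design) repeats the rule and limits it to sites with an iron participant: "an equal number of participants from each group are enrolled from each site with at least 1 participant who is assigned to iron supplementation". When one group is over-supplied at a site, "randomization will be used to select the individuals to enroll in the trial to maintain balance over time". This is random selection of whom to enrol. Group itself is not randomised: SAP 2.2 says that "the 2 groups will be determined based on the need for iron supplementation, so the treatment is not assigned by randomization".

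**Analysis.** SAP 7.2.1 fits a linear model for 4-month haemoglobin: "The set of explanatory variables will be group membership (i.e., received iron supplementation at enrolment or not), screening haemoglobin, sex, and age". The Protocol (Quantitative Data Analysis) has the same model, with baseline haemoglobin in place of screening haemoglobin. Site is also absent from the secondary efficacy models (SAP 7.2.2), the weighting predictors (7.2.3) and the subgroup models (7.2.4). No reason is given.

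**Site.** Neither document defines site for this purpose, counts the trial sites or gives a between-site variance. The nearest figure is that the centre "annually collects voluntary blood donations from 200-300 blood donor groups" (SAP 1.2, Study site and Population).

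**The concern.** Site is used to build the two groups. With equal numbers per group at each site, a site's average haemoglobin level adds equally to both group means and cancels from their difference. A model without site still counts that between-site variation as residual noise, so the reported standard error of the group coefficient is larger than its true sampling error.

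Between-site variation is plausible here. The donor groups range over religious, educational, corporate, community and walk-in sources. The SAP itself lists socio-economic status and diet as possible confounders (7.2.3), and neither is in the primary model.

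What is at stake is the width of the interval compared with the 1 g/dL margin. The validity of the non-inferiority claim is not in question.

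**Working it through.** **Step 1: the plan's own figures.** Inputs from SAP 2.4: margin 1.0 g/dL, SD 1.89 g/dL, true difference -0.3 g/dL, one-sided alpha 0.025, power 85%.

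n per arm = 2 × SD² × (z₀.₉₇₅ + z₀.₈₅)² / (margin - 0.3)² = 2 × 1.89² × (1.960 + 1.036)² / 0.7² = 130.9, rounded up to 131.

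The same formula gives 65, 80, 101 and 179 for the other rows of Table 3, as printed. Then 262 / 0.9 = 291.1, which becomes 292 in two equal arms. All stated sizes reproduce. The SD is the marginal one, so the calculation takes no credit for site or any covariate.

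**Step 2: the simple balanced case, with no covariates.** SE = 1.89 × √(2/131) = 0.2335, and the 95% half-width is 0.460 g/dL. With perfect balance, removing site multiplies the SE by about √(1 - ICC). The factor is 0.975 at ICC 0.05 and 0.949 at ICC 0.10, so the interval narrows by 2.5% and 5%.

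**Step 3: the planned model, which includes screening haemoglobin.** Group is set largely by haemoglobin and ferritin, so it is strongly collinear with screening haemoglobin. Assumptions, none of them given in the documents:
- Groups split at the haemoglobin median.
- Correlation of 0.6 between screening and 4-month haemoglobin.
- Sex and age left out.
- ICC defined on the residual variance after screening haemoglobin.
- Site variance treated as known in the random-intercept fit.

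Under a median split, the squared correlation of group with screening haemoglobin is 2/π = 0.637, so the variance inflation is 1/(1 - 0.637) = 2.75. The SE becomes 0.2335 × √(2.75 × (1 - 0.6²)) = 0.2335 × 1.327 = 0.310.

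Results for 66 sites with two per group at each (264 participants):

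| Residual ICC | SE reported by planned model | True SE of planned estimate | SE with random site intercept | Reduction against reported SE |
|---|---|---|---|---|
| 0 | 0.310 | 0.310 | 0.310 | 0% |
| 0.05 | 0.311 | 0.308 | 0.308 | 1.1% |
| 0.10 | 0.311 | 0.305 | 0.303 | 2.6% |
| 0.20 | 0.310 | 0.299 | 0.290 | 6.5% |

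The planned model's own overstatement (column 2 against column 3) is about 0.9% of the reported SE at ICC 0.05 and 1.8% at ICC 0.10. Over 10 to 131 sites, the random-intercept reduction is 1.0-1.7% at ICC 0.05 and 2.2-3.9% at ICC 0.10.

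**Step 4: does loss of balance change this?** With 10% of controls removed at random, as a rough stand-in for the exclusion of controls who start iron, the reductions for 66 sites are 0%, 1.1%, 2.5% and 6.2%. The planned SE remains at or above the true SE throughout.

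**Step 5: fixed site effects instead.** The ratio of the half-width with site dummies to that without site, over ICC 0.10 to 0, is:
- 10 sites: 0.96 to 1.01
- 26 sites: 0.98 to 1.03
- 65 sites: 1.05 to 1.10
- 131 sites: 1.23 to 1.29

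With many small sites, dummies cost more than they save.

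**The case against.** The strongest objection is that nothing stated in the plan fails. The 131 per arm uses the marginal SD, so the 85% power never counted on site. If the residual site ICC is zero, there is nothing to gain. The rule of analysing by the balancing factor comes from stratified randomisation, whereas here group is defined by iron status and randomisation only selects whom to enrol. Once screening haemoglobin is in the model, group is no longer orthogonal to site and much of the benefit of balance disappears. All of this stands. It limits the point to a small and conditional gain.

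A reader might infer four stronger things, which the documents do not support:

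- **That the interval is certainly too wide.** This needs a positive residual ICC, and the documents give none.
- **That the loss follows the simple √(1 - ICC) rule.** That rule compares two unadjusted means. With screening haemoglobin in the model, the overstatement of the planned SE is well under half as large.
- **That the trial is underpowered, or its error rate inflated, because site is missing.** The stated power does not use site. Where the omission matters, it makes the reported SE too large, which is the conservative direction.
- **That exclusions let site differences bias the group coefficient.** This could happen if exclusions cluster by site, but nothing in the documents allows its size to be judged. A random intercept would reduce such an effect without fully removing it.

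**Conclusion.** The point holds as a minor, conditional matter of efficiency. The plan balances enrolment on site and then ignores site in the primary and secondary models without saying why. If 4-month haemoglobin varies between sites beyond what screening haemoglobin, sex and age explain, the planned SE is slightly conservative. For a residual ICC of 0 to 0.10, a random intercept would make the SE about 0 to 4% smaller, depending on the number of sites; at ICC 0.20 with 66 sites of four, about 6%. These sizes rest on the assumed site layout, the correlation of 0.6 and the median split. No stated figure is wrong.

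**What to change.** In SAP 7.2.1:
- Define recruitment site, for example as the donation session at which the participant was screened.
- Add a random intercept for site to the primary linear model, with Kenward-Roger or Satterthwaite degrees of freedom.
- Do not enter site as fixed dummies.

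Use the same term in the two continuous secondary models in 7.2.2 (change in haemoglobin and ferritin). Report the estimated site ICC, which would also help in planning the UH3 phase. If site is to stay out, state the reason.

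The group coefficient and the 1 g/dL margin keep their meaning. The cost is a few lines of SAP text and a slightly more complex fit. The SAP (1.1) allows updates until it is finalised before database lock. Site is not among the baseline characteristics listed in SAP 3.4, so confirm that it is in the database; balancing by site implies that it is known at enrolment. If the site variance is estimated as zero, the model reduces to the planned one and nothing is gained.
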